There is substantial experimental evidence, biological rationale, and supportive clinical evidence to suggest the efficacy of the PHARLAP ventilation strategy in ARDS. However, mostly because of concern that SRM's and high PEEP may cause barotrauma and haemodynamic instability in critically ill patients, previous trials may have been sub-optimally designed to determine the true efficacy of such an OLS. The PHARLAP strategy is more intensive, more individual patient tailored and at least as safe as previously studied open lung strategies. In addition, the PHARLAP strategy can be delivered by almost any clinician using any conventional mechanical ventilator and if proven effective and safe, would be highly applicable for widespread use (including the developing world). Given the significance and cost of ARDS, the possible benefits of this strategy, the growing number of recommendations for the use of a LRM with elevated levels of PEEP^{18,19,46}, this study is an important undertaking. The trial will determine whether the PHARLAP ventilation strategy is effective in increasing ventilator free days in patients with ARDS. If the PHARLAP strategy is proven to improve ventilator free days it will provide a strong impetus to conduct an international phase III RCT to determine the effects of this strategy on mortality.

OBJECTIVES

Aim

To determine the efficacy of the PHARLAP strategy compared to a control ventilation strategy in increasing ventilator free days assessed during the 28 days post randomisation.

Hypothesis

The PHARLAP strategy group will have a higher number of ventilator free days at day 28 than the control group.

STUDY OUTCOME MEASURES

Primary outcome

- Number of ventilator free days at day 28 post randomisation

Secondary outcome

- Physiological outcomes:
 - PaO₂/FiO₂ ratio
 - Static lung compliance
- Inflammatory outcomes:
 - Baseline to day 3 change in IL-8 and IL-6 concentrations in broncho-alveolar lavage fluid
 - Baseline to day 3 change in IL-8 and IL-6 concentrations in plasma
- Clinical/patient-centred efficacy outcomes:
 - Use of rescue therapies for severe hypoxaemia – inhaled nitric oxide, inhaled prostacyclin, prone positioning, high frequency oscillatory ventilation and extracorporeal membrane oxygenation (ECMO)
 - Incidence of acute kidney injury (AKI)
 - ICU and hospital length of stay
 - Quality of life assessment (SF-36v2 and EQ-5D) at 6 months
 - Mortality at ICU/hospital discharge, 28 days, 90 days and 6 months

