A protocol deviation is an unanticipated or unintentional departure from the expected conduct of an approved study that is not consistent with the current research protocol or consent document. A protocol deviation may be an omission, addition or change in any procedure described in the protocol.

Given that investigators are responsible for patient safety and care, they may implement a deviation from, or a change of, the protocol to deal with an immediate hazard to trial patients without prior HREC approval. The implemented deviation or change must be reported in a protocol deviation form. The deviation must be reported by the principal investigator using the case report form so that it can be reported to the coordinating centre and the HREC (if applicable).

STATISTICAL CONSIDERATIONS

Power calculations and sample size

Based on data from the PHARLAP pilot study, with 282 subjects this study will have an 80% power to detect a difference equal to 33% of a standard deviation (equal to 3VFD's) with a two sided p-value of 0.05. To account for likely occurrence that VFD will not follow a normal distribution, the sample size has been inflated by 15% to 324 in accordance with Lehmann⁵⁶. Allowing for up to a 5% rate for withdrawal or loss to long term follow up, 340 patients will be enrolled.

Statistical and analytical plan

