Independent senior statisticians at Monash University will perform data analysis. Baseline and outcome variables will be compared using Chi-square tests for categorical variables, Student's t-test for normally distributed continuous variables and Wilcoxon rank-sum tests for non-normally distributed continuous variables. Duration of ventilation will be analysed using Cox-Proportional Hazards regression with deceased patients censored at death, allowing for results to be reported using Kaplan Meier curves. Furthermore, duration of ventilation will be stratified into survivors and non-survivors. If as expected, the duration of ventilation in each strata is well approximated by a log-normal distribution, this will enable log-transformed duration of ventilation to be analysed using parametric analysis (student t-tests) and reported as a ratio (95%CI). If normality cannot be achieved then the data would subsequently be analysed non-parametrically. Should any baseline imbalances be found to exist between groups, additional sensitivity analysis will be performed using Cox Proportional Hazards regression adjusting for imbalanced covariates. All analyses will be intention-to-treat. A complete statistical analysis plan will be finalised prior to study completion.

Interim analysis

One midpoint interim analysis (after primary outcome data is available for 170 patients) will be performed to assess accumulated safety data. This will be reported to the Data Safety Monitoring Committee, but will not be made available to the Management Committee or to study sites.

Subgroup analyses

We plan to compare study outcomes in the following pre-specified subgroups:

- (a) Patients with severe ARDS ($\text{PaO}_2/\text{FiO}_2 < 100$) versus patients with moderate ARDS ($\text{PaO}_2/\text{FiO}_2$ 100-200 mmHg) at enrolment.
- (b) Patients with diffuse ARDS versus patients with focal ARDS at enrolment (determined by independent radiologists).
- (c) Patients who are responders to the open lung strategy versus patients who are non-responders (defined as meeting lack of improvement in static lung compliance definition).

SAFETY OF SUBJECTS

Data Safety Monitoring Committee

An independent Data Safety Monitoring Committee, comprising experts in clinical trials, biostatistics and intensive care will be established. The committee will be responsible for monitoring mortality related to serious adverse events, serious adverse events and reviewing the interim safety analysis.

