APPENDIX 7: DIFFUSE VERSUS FOCAL ARDS SUBSTUDY

This is a study to determine if acute respiratory distress patients with different subtypes behave differently.

Background & rationale

Patients with different subtypes of ARDS (focal, diffuse and patchy (on Chest X Ray)) may behave differently with application of high vs low PEEP depending on the percent of recruitable lung and the amount of stress and strain during PEEP titration/recruitment.

Patients with diffuse ARDS appear to have more recruitable lungs (1), have a higher inflection point and require higher PEEP levels for adequate recruitment without causing over-distension whereas patients with focal ARDS develop over-distension with higher levels of PEEP and have less recruitable lungs (2,3). Accordingly, in patients with a focal distribution of loss of aeration (i.e., with atelectatic dependent lobes coexisting with aerated nondependent lobes), the use of high PEEP levels (15–20 cm H₂O) results in minimal alveolar recruitment in the dependent lobes but significant hyperinflation in the nondependent lung lobes. Patients with patchy ARDS lie in between the two above mentioned subgroups (Table 1).

	Incidence (n=71)	Mortality rate	Primary ARDS	Compliance (ml cm H ₂ O ⁻¹)	Lower Inflection Point (cm H ₂ O)
Diffuse	23% (16)	75%	82%	19±9	8.4±2
Focal	36% (26)	42%	50%	41± 21	4.6±2
Patchy	41% (29)	41%	79%	30±15	6.3±2.7

Table 1. Differences between the 3 subgroups of patients with ARDS (Puybasset et al) (2,4,5)

Patients can be identified *a priori* as either having focal, patchy or diffuse disease based on their chest radiograph at the time of ARDS diagnosis/ study inclusion. The PHARLAP study provides an excellent opportunity to prospectively examine the effect of PEEP and recruitment on lung injury in the different subgroups as there will measurement of blood and bronchoalveolar lavage cytokines levels as a part of the study.

Objectives

Aim

To investigate the effect of recruitment and high (PHARLAP) v low (conventional) PEEP levels on inflammatory markers in different subtypes of ARDS (based on CXR).

Hypothesis

Patients with diffuse ARDS, when randomized to the recruitment and high PEEP arm, will have lower inflammatory markers when compared to patients ventilated with conventional ARDSnet protocol (6) as used in the LOVS study (7).

Study outcome measures

Analyse the inflammatory outcomes based on the radiological type of ARDS.

Inflammatory markers will be measured by

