As PHARLAP proposes to include 340 patients, based on previous studies (2,4,5,8) about one third of patients will fall into each group and this should still leave adequately sized groups of patients with focal, patchy and diffuse to study their influence on the PHARLAP primary outcome of number of ventilator free days at day 28 post randomisation, markers of inflammatory mediators, and several other secondary outcomes. With a total of 300 patients in the study based on data from [name] et al (8) –personal communication we will likely get 80-100 patients per subtype, which would mean approximately 40 to 50 patient in each arm per subgroup. This should give us a reasonable sample size for each subgroup, and whilst mortality differences or VFDs may be unlikely, the potential for differences in other outcomes is reasonable, beside it will generate hypothesis for future studies.

We plan to analyse the outcomes of the study by utilising the general linear model with each outcome primary and secondary outcomes (PHARLAP - primary and secondary outcomes analysed separately as the dependent variable while ventilation strategy (PHARLAP / control), CXR coding (diffuse, focal, patchy) will be entered as independent factors. Interaction between ventilation strategy and the CXR coding will also be studied in the model. Post Hoc analysis will be done between the various CXR and ventilation subgroups (it will compare the outcomes of the CXR subgroups (diffuse, patchy and focal) within and among the PHARLAP and control group).

Funding

Diffuse versus focal substudy is supported by a \$34 950 grant (ANZCA) for procurement of the Chest X rays, cost of independent radiological scoring, statistical advice and salary support for a research assistant based at the ANZIC-RC.

Publications

A separate publication following the main publication will be completed in the name of the PHARLAP investigators led by [name] and the PHARLAP writing committee.

References

1. Nieszkowska A, et al. Incidence and regional distribution of lung over inflation during mechanical ventilation with positive end-expiratory pressure. *Crit Care Med* 2004; 32:1496–1503
2. Puybasset L, et al. Regional distribution of gas and tissue in acute respiratory distress syndrome. III. Consequences for the effects of positive end-expiratory pressure. *Int Car Med* 2000;26:1215-1227

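### The substudy's single linear model cannot be fitted to cause of death, can cost power on raw IL-6/IL-8 change if levels are skewed, and can misstate error in within-subtype contrasts of binary outcomes

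*Combined protocol and SAP*

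**What the plan says.** Appendix 7, Statistical considerations, sets out the substudy analysis as "utilising the general linear model with each outcome primary and secondary outcomes", each taken separately as the dependent variable. Ventilation strategy and chest X-ray class (diffuse, focal, patchy) are the factors. It adds that "Interaction between ventilation strategy and the CXR coding will also be studied in the model" and that "Post Hoc analysis will be done between the various CXR and ventilation subgroups". It expects "approximately 40 to 50 patient in each arm per subgroup". It names no link function, transformation, baseline covariate, robust variance or non-parametric fallback.

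The outcomes it takes in are those of the main protocol. Under Secondary outcome these include "Mortality at ICU/hospital discharge, 28 days, 90 days and 6 months", rescue therapy use, acute kidney injury, barotrauma, lengths of stay and cause of death. Appendix 7 states the cytokine outcomes as baseline-to-day-3 change in IL-6 and IL-8 concentration. Its hypothesis is that inflammatory markers will be lower under PHARLAP in diffuse ARDS.

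The main plan treats the same variables by type. Power calculations and sample size allows for the "likely occurrence that VFD will not follow a normal distribution". Statistical and analytical plan uses chi-square tests for categorical variables and "Wilcoxon rank-sum tests for non-normally distributed continuous variables". It also log-transforms duration of ventilation, with a non-parametric fallback.

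**The concern.** A general linear model assumes a numeric response with roughly constant residual variance. Three features of the substudy strain that.

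- Cause of death is nominal, so no linear model of it exists.
- Cytokine concentrations are often right-skewed. If they are here, a few extreme values dominate the variance of a raw change, and a real effect on the substudy's main question can be missed.
- For a binary outcome the variance is p(1 − p), so it differs between subtypes with different event rates. A contrast within one subtype that uses the model's pooled residual variance then has the wrong standard error.

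At stake is whether the substudy can answer its own inflammatory question, and whether the p-values in its post hoc subtype comparisons mean what they say. The trial's primary comparison is not involved.

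**Working it through.** **Cell sizes.** Appendix 7's figure follows from its own inputs: 80 to 100 patients per subtype ÷ 2 arms = 40 to 50. Its Table 1 ("Differences between the 3 subgroups of patients with ARDS") has 16 of 71 patients diffuse, which gives fewer: 16/71 × 340 / 2 = 38.3, so about 38 per arm. BAL samples may be fewer still, since the protocol lets a site omit them.

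**Cause of death.** No arithmetic applies. It is a listed secondary outcome, the model is stated for each outcome, and the outcome has no numeric value to regress.

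**Cytokines within diffuse ARDS.** The documents give no SD, correlation or expected effect, so all of these are assumptions: lognormal levels, log-scale correlation 0.5 between baseline and day 3, day-3 level halved under PHARLAP and unchanged under control, 38 per arm, two-sided 5%. Simulated power of the two-arm comparison:

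| Analysis | log-SD 0.5 | log-SD 1.0 | log-SD 1.5 |
|---|---|---|---|
| Raw change, unadjusted | 99% | 45% | 15% |
| Raw day-3 level, adjusted for baseline | 100% | 73% | 27% |
| Log day-3 level, adjusted for log baseline | 100% | 93% | 62% |

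The last row can be checked by hand. The effect is ln 2 = 0.693. The SE is s × √(1 − 0.5²) × √(2/38) = 0.199s, where s is the log-SD. At s = 1.0 the ratio is 0.693/0.199 = 3.49, and at s = 1.5 it is 2.33. Against a critical value of about 1.99, these give about 93% and 63%.

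At log-SD 1.0 the total gain is 93 − 45 = 48 points, of which 73 − 45 = 28 come from baseline adjustment without any transformation. At log-SD 1.5 the total is 47 points, of which 12 come from adjustment. At 45 per arm, inside the appendix's stated range, raw change against adjusted log level is 49% v 96% and 17% v 71% at log-SD 1.0 and 1.5.

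With no true effect, the raw-change test rejects in about 3.3% to 5.0% of runs. The fault there is lost power, not false positives.

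**Binary outcomes, contrast within diffuse ARDS.** Take 300 patients at the Table 1 mix: 34, 54 and 62 per arm for diffuse, focal and patchy.

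- Table 1 mortality 75%, 42%, 41%. The variances p(1 − p) are 0.1875, 0.2436 and 0.2419. The pooled value is (34 × 0.1875 + 54 × 0.2436 + 62 × 0.2419)/150 = 0.230. The true-to-assumed SE ratio is √(0.1875/0.230) = 0.90. The nominal cut-off of 1.96 is really 1.96/0.9025 = 2.17, a true error of about 3.0%.
- Assumed lower mortality 35%, 22%, 20%. The variances are 0.2275, 0.1716 and 0.1600, pooled 0.1795. The ratio is √(0.2275/0.1795) = 1.126. The effective cut-off is 1.96/1.126 = 1.74, a true error of about 8.2%.

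Simulation agrees: 2.6% to 3.5% in the first case, and about 8% to 9% in the second.

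**VFDs and overall tests.** Simulating the full two-by-three model with no true effect, the arm test rejects in 4.8% to 5.3% of runs for mortality and 4.7% to 5.3% for VFDs. With equal cells the interaction test rejects in 4.8% to 5.2% for these two. With unequal cells it ranges from 4.5% to 6.3% for mortality and 4.2% to 5.0% for VFDs. For power at 50 per cell, with VFD zeros assumed at 60%, 40% and 40%, the linear model against a stratified rank test gives 48% v 47%, 23% v 24% and 50% v 51% under three effect patterns. For diffuse mortality of 75% v 50%, the linear contrast has 74% power and the chi-square test 75%.

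**The case against.** The strongest reply is that a linear model is more robust than it looks. The figures bear this out for VFDs and mortality: the overall tests stay near nominal and lose no material power. A reader might infer from the mixture of outcome types that every substudy test is invalid or underpowered. The documents do not support that.

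A reader might also infer that the appendix contradicts the main plan. That is weak. Chi-square and rank-sum tests compare two groups and give no interaction test, so a substudy about interaction needs a different model. Nor is the main plan's method the best available for cytokines: a Wilcoxon test on the same raw change has about 63% and 34% power at log-SD 1.0 and 1.5, below the adjusted log analysis.

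The size of the cytokine loss does rest on assumptions. At log-SD 0.5 almost nothing is lost, and part of any gain comes from baseline adjustment. This limits the claim to a conditional one but does not remove it, because the proposed analysis costs nothing when skewness is mild.

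Finally, the substudy describes itself as generating hypotheses and expects no VFD or mortality differences. The protocol also promises a complete SAP, and the substudy grant covers statistical advice. These lower the severity. None of them states a model for the substudy, and the SAP sentence does not mention it.

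**Conclusion.** The point holds in a limited form, and its severity is minor.

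- The stated method cannot be fitted to cause of death. This needs no assumption.
- For IL-6 and IL-8, unadjusted raw change could cut power from about 93% to 45%, or from 62% to 15%, if log-SD is 1.0 or 1.5. It loses almost nothing at 0.5. This rests on lognormal levels, correlation 0.5, a true halving and 38 per arm, none of which except the cell size can be traced to the documents.
- Pooled-variance contrasts within a subtype can be off for binary outcomes, in either direction: about 3% at the Table 1 mortality rates and 8-9% at the assumed lower rates. Cytokine contrasts could be further off if spread differed by subtype. With log-SD assumed at 1.5, 1.0 and 0.8, simulated error in the diffuse contrast was 24% to 33%, but the documents give no spread by subtype.

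There is no ground for saying that VFD or mortality analyses lose power, or that the overall arm tests have wrong error rates. The trial's primary analysis is unaffected.

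**What to change.** Replace the single-model sentence in Appendix 7 with a short paragraph by outcome type:

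- IL-6 and IL-8: log day-3 level adjusted for log baseline, with strategy, chest X-ray class and their interaction.
- Binary outcomes: logistic regression with the same terms.
- Cause of death: descriptive table only.
- Within-subtype contrasts: robust or subtype-specific variances, taken from the interaction model.

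An ordinal or rank-based model for VFDs is optional, since little would change.

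The cost is one paragraph and standard software, with no new data. Cytokine effects would be reported as ratios rather than differences, and values below the assay limit need a stated rule. Settling this before the data are analysed by arm also avoids choosing models after seeing the results.

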Site personnel will enrol patients using an internet-based system hosted by the ANZIC Research Centre. Randomisation to either the PHARLAP group or the control group will be by permuted blocks and stratified for centre and for the cause of ARDS (direct or indirect)⁴⁸.

Co-enrolment

Co-enrolment of patients into other interventional studies will be decided by the PHARLAP and the co-enrolling study management committees on a case-by-case basis. Participants can be co-enrolled in observational studies.

PARTICIPATING STUDY SITES

To be confirmed

- Albury Wodonga Health
- CVICU, Auckland City Hospital
- DCCM, Auckland City Hospital
- Austin Hospital
- Barwon Health (Geelong Hospital)
- Flinders Medical Centre
- John Hunter Hospital
- King Abdulaziz Medical City for National Guard (Riyadh)
- Lyell McEwin Hospital
- Middlemore Hospital
- Nepean Hospital
- Northern Hospital
- Launceston
- Prince Charles Hospital
- Royal North Shore
- Royal Prince Alfred
- St Vincents Hospital (Dublin)
- The Alfred Hospital
- Wellington Hospital
- Wollongong Hospital

STUDY PROCEDURES

Commencement of mechanical ventilation strategy

Patients in both groups should be commenced on the assigned mechanical ventilation strategy as soon as possible (but no later than 4 hours) after randomisation.

Prior to changing the pre-randomisation mechanical ventilation settings to the assigned strategy, 3 tasks need to occur in the following order in both groups of patients:

1. Predicted body weight should be estimated.
2. Static respiratory compliance should be measured (see below).
3. Specimens of blood and BAL should be collected (see below) – after static respiratory compliance has been measured.

Estimation of predicted body weight:

Before setting up the ventilator strategy, the patient's predicted body weight must be determined. This should be estimated using a formula which requires height⁴⁹ (Appendix 1). If there has been no recent (last few days) measurement of height, the height should be estimated using a formula which requires measurement of the demi-arm span (Appendix 1).

Measurement of static respiratory compliance:

- The patient should be adequately sedated (no spontaneous breaths).
- An expiratory pause of 5 seconds should be set to measure intrinsic PEEP (PEEPi). If the 5 second pause can not be achieved (because the next breath occurs before the end of the pause), a shorter pause should be set.
- Total PEEP is calculated as PEEPi + set PEEP.

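### The substudy model for CXR subtype leaves out cause of ARDS, so it cannot show whether a difference in response between subtypes is due to radiographic pattern or to cause

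*Combined protocol and SAP*

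**What the plan says.** Appendix 7, Statistical considerations, specifies a general linear model for each primary and secondary outcome: "while ventilation strategy (PHARLAP / control), CXR coding (diffuse, focal, patchy) will be entered as independent factors". It adds: "Interaction between ventilation strategy and the CXR coding will also be studied in the model". Post hoc comparisons of the subtypes, within and across the two arms, follow. The expected size is "approximately 40 to 50 patient in each arm per subgroup". The appendix says that differences in mortality or ventilator-free days (VFDs) may be unlikely and that the substudy will generate hypotheses.

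Table 1 of the appendix ("Differences between the 3 subgroups of patients with ARDS", 71 patients from earlier work) lists subtype, incidence with count, mortality and percentage with primary ARDS. Its rows begin as follows, the last figure being the primary ARDS percentage:

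- "Diffuse 23% (16) 75% 82"
- "Focal 36% (26) 42% 50"
- "Patchy 41% (29) 41% 79"

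The appendix's one stated hypothesis compares the two strategies within diffuse ARDS.

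In the main protocol, Enrolment and randomisation says allocation is "stratified for centre and for the cause of ARDS (direct or indirect"). Data variables collected lists cause of ARDS. The only covariate adjustment, under Statistical and analytical plan, is a sensitivity analysis for baseline imbalance between the treatment groups. That section also defers to a complete SAP to be finalised later.

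**The concern.** CXR subtype is observed, not randomised. If subtypes differ in their mix of direct and indirect ARDS, and the strategy works differently by cause, a model without cause carries part of the by-cause difference into the strategy-by-subtype term. Stratified randomisation balances cause between the arms, but it does not separate cause from subtype. The planned adjustment for imbalance between arms does not do so either.

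Comparisons of subtypes within one arm are more exposed still. There, a purely prognostic effect of cause is enough to produce a difference.

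What is at stake is attribution. The rationale in Appendix 7 is mechanistic: it links radiographic pattern to recruitable lung and over-distension. A difference between subtypes would naturally be read as support for that mechanism and carried into the hypotheses for later studies.

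**Working it through.** **1. The plan's own figures.** Power calculations and sample size equates 0.33 SD with 3 VFDs, so the SD is 3/0.33 = 9.1 VFDs. With two-sided 5% and 80% power, a standardised difference of 0.334 needs 282 patients in total, 1/3 needs 284 and 0.33 needs 290. The stated 282 is reproduced within 3%. For the substudy, 300/3 = 100 per subtype and 100/2 = 50 per arm, the top of the stated 40 to 50.

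**2. How firm the link in Table 1 is.** The percentages correspond to about 13/16 diffuse, 13/26 focal and 23/29 patchy patients with primary ARDS.

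- Diffuse minus focal: 0.82 - 0.50 = 0.32. Standard error = sqrt(0.82 x 0.18/16 + 0.50 x 0.50/26) = 0.137, so the 95% interval is about 0.05 to 0.59. Fisher p = 0.056.
- Diffuse against patchy: Fisher p = 1.0.
- All three groups: chi-square p = 0.031.

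**3. Carry-over.** Assume primary means direct and the trial has Table 1's mix. Let D be the treatment effect in direct ARDS minus that in indirect ARDS, and p the direct share in a subtype. If pattern itself has no influence on the effect, the effect in a subtype is the indirect effect + p x D. Two subtypes then differ by (difference in p) x D:

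| Contrast | Difference in p | Carried over |
|---|---|---|
| Diffuse - focal | 0.82 - 0.50 | 0.32 D |
| Patchy - focal | 0.79 - 0.50 | 0.29 D |
| Diffuse - patchy | 0.82 - 0.79 | 0.03 D |

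The same algebra applies within one arm. A prognostic gap P between direct and indirect ARDS appears as 0.32 P in diffuse minus focal, even when D = 0.

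**4. On the VFD scale.** The documents give no value for D, so a range is shown. The standard error of the diffuse-focal interaction with m patients per cell is 9.1 x sqrt(4/m), which is 2.9 VFDs for m = 40 and 2.6 for m = 50.

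| Assumed D (VFDs) | 0.32 D (VFDs) | Contrast significant at 5% |
|---|---|---|
| 3 | 0.96 | 6-7% |
| 6 | 1.92 | 10-12% |
| 9 | 2.88 | 17-20% |

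With the interval from step 2, D = 3 gives 0.05 x 3 = 0.15 to 0.59 x 3 = 1.77 VFDs.

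**5. Simulation of three models.** Settings: 45 per cell, 3,000 trials per scenario, an effect in direct ARDS only, and none from pattern at a given cause. Entries are the mean diffuse-focal interaction in SD, with the rejection rate of the 2-df interaction test.

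| D (SD) | As planned | Plus cause | Plus cause and strategy-by-cause |
|---|---|---|---|
| 0.33 | 0.10; 6% | 0.10; 6% | about 0; 5% |
| 0.67 | 0.22; 10% | 0.22; 10% | about 0; 5% |
| 1.0 | 0.31; 15% | 0.31; 16% | about 0; 5% |

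A main effect of cause does not help, because it shifts both arms of a subtype alike.

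**6. Which D is plausible.** About 49/71 = 69% of Table 1's patients are primary. An effect of 1 SD in direct ARDS only would mean 0.69 SD overall, about twice the design effect of 0.33 SD. An effect of 0.5 SD would mean about 0.35 SD overall, close to the design effect. With Table 1's mix applied to 340 patients (38, 62 and 70 per arm), D = 0.5 SD gives a carry-over of about 0.15 SD and a diffuse-focal rejection rate of about 8-9%, against about 5% in the fuller model.

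**7. Precision cost.** At D = 0.5 SD and 38, 62 and 70 per arm, the interaction standard error rises from 0.295 to 0.303 SD (about 3%). At 45 per cell the rise is about 4-5%.

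**The case against.** A reader might infer that any treatment effect differing by cause would be reported as a subtype difference, and that the rates above are false positives. The documents do not support that, for five reasons.

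- **The contrast is real as description.** If the strategy works only in direct ARDS and diffuse disease is mostly direct, the effect does differ between diffuse and focal patients. The aim in Appendix 7 concerns effects in different subtypes; it does not define an effect of pattern independent of cause. The error would lie in the attribution.
- **The stated hypothesis is not confounded.** It compares randomised arms within diffuse ARDS. Subtype is read from a film at diagnosis or inclusion, and allocation is stratified by cause.
- **The carry-over is partial and seldom significant.** It is about a third for diffuse-focal and almost nil for diffuse-patchy. The larger rejection rates need an implausible effect.
- **The evidence is thin.** It comes from 71 outside patients, only 16 of them diffuse, and the appendix does not define primary.
- **The substudy is exploratory, and a complete SAP is to follow.** No patient selection rule is proposed.

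All of this stands, and it limits the point to interpretation. It does not remove it. The rationale is mechanistic, so attribution to pattern is the likely reading of a difference. Comparisons of subtypes within an arm lack the protection that randomisation gives the within-diffuse contrast. Nothing in the documents commits the later SAP to including cause.

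**Conclusion.** The point holds in a limited form. The planned interaction validly describes how effects differ between subtypes, but it cannot show whether a difference is due to radiographic pattern or to cause. Under Table 1's mix, 0.32 of any by-cause difference in effect enters diffuse minus focal (95% interval about 0.05 to 0.59), 0.29 enters patchy minus focal and 0.03 enters diffuse minus patchy. At an effect near the trial's design value this is mainly a bias in what the estimate is taken to mean, with a small rise in rejection rate.

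This rests on three assumptions: primary in Table 1 means direct in the randomisation strata, the trial's mix resembles Table 1, and the effect differs by cause by an amount that the documents do not give. It would go too far to say that the substudy's results will be wrong, or that later trials would select patients by the wrong feature. No such conclusion or selection is stated, and pattern would still partly predict response. This is an inexpensive improvement to consider; it does not touch the main trial's comparison.

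**What to change.** In Appendix 7, Statistical considerations, keep the planned model and prespecify a supporting analysis that adds cause (direct or indirect) and the strategy-by-cause interaction. Both terms should be named: a main effect of cause addresses prognostic differences within an arm but leaves the carry-over into the interaction. Report both models with estimates and intervals. State in advance that a difference in response will be attributed to CXR pattern itself only if the strategy-by-subtype estimate is similar in the supporting model. Also state whether primary in Table 1 corresponds to direct in the strata.

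The cost is a short addition to the text and no new data, since cause must be known at randomisation. The interaction standard error grows by about 3 to 5% with complete data. It will grow more where BAL samples are missing, which the protocol allows, or where indirect diffuse patients are few: under Table 1's mix, about 0.18 x 38 = 7 per arm. For such outcomes the supporting model may be too imprecise to settle attribution, and the report should then say so.
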